RATIONALE	National Guidelines specify that one treatment option for newly diagnosed intermediate and high-risk prostate cancer patients is external beam radiation therapy (RT) plus 6-24 months of concomitant androgen deprivation therapy (ADT). This standard of care combination therapy demonstrates significant survival benefits. ADT effectively slows the growth of prostate cancer cells, thereby enhancing the therapeutic effectiveness of RT. Despite the clinical gains, ADT leads to an array of side effects including insulin resistance, dyslipidemia, weight gain, increased visceral fat mass coupled with increased muscle wasting/sarcopenia, and quality of life deterioration. These metabolic and physiologic changes begin rapidly within the first few months of ADT use and place patients at increased risk of new co-morbidities such as diabetes, cerebrovascular disease, coronary artery disease, venous thromboembolism and sudden cardiac death. Identifying translational approaches to attenuate these ADT metabolic aberrations have not been rigorously tested, leaving a gap in determining patient treatment options. This proposal pilot tests a comprehensive nutrition and physical activity intervention initiated concurrently with RT+ADT in newly diagnosed intermediate and high-risk prostate cancer patients to determine whether the intervention intercepts the abrupt metabolic and physiologic changes caused by ADT.
STUDY DESIGN	This is a pilot randomized controlled trial to investigate the effects of a 6-month nutrition and physical activity intervention on blood measures of lipids and insulin resistance, and anthropometry, body composition, and patient reported outcomes in newly diagnosed intermediate and high-risk prostate cancer patients undergoing RT+ADT.
PRIMARY OBJECTIVE	The study has the following primary specific aims : 
 
1. Examine intervention effects on ADT-induced insulin resistance measured by HOMA-IR;
 
2. Examine intervention effects on ADT-induced changes in anthropometry and body composition;
 

SECONDARY OBJECTIVES	Exploratory aims: 
 
1. Explore intervention effects on blood lipids (triglycerides and total, HDL- and LDL-cholesterol) and hemoglobin A1c;
 
2. Explore intervention effects on patient reported outcomes.
 
3. Explore intervention effects on the gut microbiome
 

NUMBER OF SUBJECTS	20
SUBJECT SELECTION CRITERIA: Inclusion Criteria	Inclusion Criteria: 
 
1. Males aged 40 or older with newly diagnosed D'Amico risk category intermediate or high-risk prostate cancer;
 

	
 
2. Primary treatment is external beam radiation therapy with androgen deprivation therapy [Zoladex, Lupron, Degarelix, and other luteinizing hormone-releasing hormone (LHRH)-directed therapies];
 
3. Physically able to undertake an exercise program.
 

SUBJECT SELECTION CRITERIA: Exclusion Criteria	Exclusion Criteria: 
 
1. Advanced, metastatic disease;
 
2. Planning to join a commercial/structured diet change or fitness program;
 
3. Have significant pre-existing T2D (poor glycemic control while on medication, Hemoglobin A1c <math>\geq 10</math>) or significant pre-existing CVD (myocardial infarction or stroke within prior six months);
 
4. Physician confirmed cognitive impairment or alcohol/narcotic abuse;
 

DURATION OF SUBJECT PARTICIPATION AND DURATION OF STUDY	Subjects will participate in the study for 6 months. The total duration of the study is expected to be 1.5 years
PRIMARY ENPOINTS	
Primary Aim 1: Compare intervention effect HOMA-IR levels relative to baseline in intervention and control participants.
 
Primary Aim 2: Compare intervention effect on weight, waist circumference, fat mass and lean mass relative to baseline in intervention and control participants.

SECONDARY ENDPOINTS	Exploratory Aims. We will explore the intervention effect on blood lipids and HbA1c, and whether the intervention induces patient reported outcomes (PROs)-specifically quality of life and fatigue differences between the intervention and control arms
STATISTICS Primary Analysis Plan	Linear regression models will test the intervention effects on ADT-induced changes in HOMA-IR ( Aim 1 ), body composition ( Aim 2 ) and metabolic biomarkers, PRO measures and gut microbiome ( Exploratory aims ). Separate models will be fit for each outcome measure, with an indicator variable for study arm (intervention/control) and adjustment for the respective baseline metabolic biomarker, body composition or PRO measure. Further adjustment for biomarkers that may have shared biology (i.e., total and LDL cholesterol) and for medication use that could affect biomarker concentrations will be considered. We expect most potential confounding variables will be evenly distributed between arms at randomization, but this assumption will be checked prior to analysis. Analyses will follow an intent-to-treat approach.
Rationale for Number of Subjects	We have set a sample size of 10 in each of the intervention and control arms for this pilot study, which will provide preliminary data to support an R01.

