#### 3.2 Exclusion Criteria

1. Advanced, metastatic disease;
2. Planning to join a commercial/structured diet change or fitness program;
3. Have significant pre-existing T2D (poor glycemic control while on medication, defined as Hemoglobin A1c of  $\geq 10$  within the prior 12 months) or significant pre-existing CVD (myocardial infarction or stroke within prior six months);
4. Physician confirmed cognitive impairment or alcohol/narcotic abuse;

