## 5.1 Outcomes

### 5.1.1 Blood Biomarkers

Blood markers of glucose, insulin, hemoglobin A1c, triglycerides and total, LDL- and HLD-cholesterol will be analyzed by the University of Minnesota Advanced Research and Diagnostics Laboratory. Homeostatic model assessment of insulin resistance (HOMA-IR) will be computed from glucose and insulin concentrations.

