## 7. DATA ANALYSIS PLAN

This pilot trial tests whether a nutrition and physical activity intervention initiated concurrently with RT+ADT will intercept ADT-induced metabolic and physiologic abnormalities compared to control. We expect clinically meaningful changes in the control arm and minimal to no changes in the intervention arm, as the primary intervention goal is prevention. To test the intervention effects for our aims, we will use this difference in differences approach, which accounts for expected temporal changes in the biomarkers and body composition measures in the control arm.

1. The effects of the intervention on ADT-induced changes in HOMA-IR will be evaluated using linear regression models with adjustment for the baseline biomarker.
2. The effects of the intervention on ADT-induced changes in body weight and composition will be evaluated using linear regression models. Separate models will be fit for each measure, with an indicator variable for study arm (intervention/control) and adjustment for the respective body composition measure.

As exploratory aims, we will explore intervention effects on blood lipids HbA1c, patient reported outcomes and gut microbiome will be evaluated using linear regression models. Separate models will be fit for each biomarker, with an indicator variable for study arm (intervention/control) and adjustment for the respective baseline biomarker. Further adjustment for biomarkers that may have shared biology (i.e. total and LDL cholesterol) and for medication use that could affect biomarker concentrations will be considered.

We expect most potential confounding variables will be evenly distributed between arms at randomization, but

this assumption will be checked prior to analysis. Analyses will follow an intent-to-treat approach; to be  
2-sided and statistical significance will be set at  $P<0.05$ .

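### Does the synopsis open the primary HOMA-IR model to optional covariates that section 7 keeps out?

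*Combined protocol and SAP*

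**What the plan says.** The synopsis (Statistics, Primary Analysis Plan) covers Aim 1 (HOMA-IR), Aim 2 (body composition) and the exploratory outcomes in one paragraph. "Separate models will be fit for each outcome measure, with an indicator variable for study arm (intervention/control"), plus the baseline value of the measure concerned. It then adds an optional step of extra covariates, worded as "biomarkers that may have shared biology (i.e., total and LDL cholesterol) and for medication use that could affect biomarker concentrations will be considered".

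Section 7 (Data Analysis Plan) takes the aims one at a time. Item 1 reads: "The effects of the intervention on ADT-induced changes in HOMA-IR will be evaluated using linear regression models with adjustment for the baseline biomarker". The optional step comes later, in the paragraph that begins "As exploratory aims, we will explore intervention effects on blood lipids HbA1c, patient reported outcomes and gut microbiome", where it is worded as "biomarkers that may have shared biology (i.e. total and LDL cholesterol) and for medication use that could affect biomarker concentrations will be considered". Section 7 ends with two-sided testing, for which "statistical significance will be set at" P<0.05.

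Both places also say that balance between arms will be checked before analysis. Section 5.1.1 says "Homeostatic model assessment of insulin resistance (HOMA-IR) will be computed from glucose and insulin concentrations".

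**The concern.** Read side by side, the optional-adjustment sentence reaches HOMA-IR in the synopsis but not in section 7, and nothing says which text governs. The medication clause could matter for this endpoint. HOMA-IR comes from glucose and insulin concentrations, and section 3.2 excludes type 2 diabetes only where there is "poor glycemic control while on medication, defined as Hemoglobin A1c of" 10 or more, so better-controlled men on glucose-lowering drugs can enrol.

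If the primary test could be run with or without medication use, and the choice were made after seeing the results, the 5% level would not hold. A reader of the pilot report might also be unsure whether a medication-adjusted HOMA-IR result was the planned one. HOMA-IR is primary aim 1, and section 6.3 says the pilot will inform the design of a fully powered trial, so the question is fair.

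**Working it through.** **1. The two texts compared**

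| | Synopsis | Section 7 |
|---|---|---|
| Base model for HOMA-IR | arm + baseline HOMA-IR | baseline HOMA-IR named; arm implied |
| Optional step | follows the pooled description of all outcomes | in the exploratory paragraph |
| Status of the optional step | to be considered | to be considered |

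The base model is the same. Section 7 does not say that baseline is the only covariate. That is an inference from a short item, which also leaves out the arm indicator, while item 2 leaves out the word baseline. The shared-biology clause is tied to total and LDL cholesterol, which are exploratory outcomes. Only medication use plausibly extends to HOMA-IR, so the realistic choice is between two models.

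**2. Inputs**

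From section 7.1: 10 per arm, SD 1.4, pre-post correlation 0.5, two-sided 5%. Assumed, because the documents give no figure: baseline medication use in 20% to 40% of men, linked to HOMA-IR by 0 to 2 units.

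The detectable difference of 2.6 in section 7.1 is not reproduced by these inputs. The change SD is 1.4 × √(2 × (1 − 0.5)) = 1.40, which gives 1.85 at 80% power; 2.62 appears only with correlation 0 (SD 1.4 × √2 = 1.98). That is a separate matter, and the error rates below do not use the 2.6.

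**3. Precision of the base model**

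Residual SD = 1.4 × √(1 − 0.5²) = 1.212. Standard error = 1.212 × √(2/10) = 0.542. The simulated mean is 0.550, slightly larger because chance baseline differences cost some precision.

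**4. Type I error by how the model is chosen (simulation, no true effect)**

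| Rule | Type I error |
|---|---|
| Baseline-only model, always | 4.9% to 5.1% |
| Fuller model with one to three extra covariates, always | 4.7% to 5.2% |
| Add medication if arm proportions differ by at least 0.2 or 0.3 | 3.0% to 5.3% |
| Run both, report the smaller P: link 0 or 1.0 unit | 5.9% to 6.2% |
| Same, covariate correlated 0.3 with the outcome | 6.8% |
| Same, 2-unit link | 7.8% to 8.0% |

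The third row is not inflated because the choice uses arm and baseline data, never the outcome. Smallest-P selection over four or eight models gives 7.1% to 8.7% or 8.4% to 12.4%, but that needs two or three optional covariates, and the plan names no extra biomarkers for HOMA-IR.

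**5. Effect on the result**

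With a link of 0 or 1.0 unit, adding medication moves the estimate by a median of 0.05 to 0.07, that is 0.05/0.55 = 9% to 0.07/0.55 = 13% of a standard error (90th percentile about 0.22 to 0.30). The P<0.05 verdict differs between the two models in 2.0% to 2.5% of trials with no effect, and in 6.6% to 8.9% at a true difference of 1.0. A stronger link would move these further.

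**The case for a change.** The best case for a change is that the same sentence has two scopes in current text, that the medication clause does apply to an index built from glucose and insulin, and that aligning the wording would cost a sentence or two. If section 7 item 1 is read as non-exclusive, the optional step reaches the primary model with no rule for using it. A pilot that sets a formal 5% test, the argument runs, should leave no doubt about which HOMA-IR estimate was planned.

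The difference in scope stands, and so does the absence of a rule. It does not follow that the 5% level depends on naming one model in advance: choosing on baseline imbalance does not raise the error, and only choosing on P values does. Nor is the planned estimate in real doubt, since both places start from the baseline-adjusted model and treat the rest as additional. Fixing medication use as a primary covariate would not be a free remedy either. The data collection listed in sections 4.2, 4.4 and 5 does not mention recording medication use, so the documents do not show that the covariate would be available.

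**Conclusion.** No change is needed. The synopsis compresses what section 7 sets out aim by aim, and in doing so it blurs how far an optional step reaches. The plan as written gives an unbiased HOMA-IR comparison at about the 5% level under either model, and under a choice based on baseline balance. Error of roughly 6% to 8% would require selection by P value with one medication covariate. That range depends on assumed prevalence (20% to 40%) and an assumed link to HOMA-IR (up to 2 units), so it illustrates the risk and is not a bound. For 20 men and preliminary data, a competent analyst would report the model with arm and baseline HOMA-IR as the primary result and present any medication-adjusted result as a sensitivity analysis. Rewriting the sentence would only record the base model that both places already give.

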## 1. BACKGROUND

Prostate cancer represents 19% of all new cancers in men with an age-adjusted incidence rate of 109/100,000. Many prostate cancers are low risk, localized tumors where the 5-year relative survival rate is 99% even without treatment. However, at least a third of prostate cancers present at diagnosis as intermediate to high-risk disease and a 2018 report noted a recent increase in incidence of these more aggressive tumors. The National Comprehensive Cancer Network (NCCN) Guidelines, the American Urological Association (AUA), the American Society for Radiation Oncology (ASTRO) and the Society of Urologic Oncology (SUO) all specify that these patients should receive curative-intent, multimodal treatment consisting of radiation therapy (RT) + at least six months of ADT. The RT+ADT combination therapy gives clinically important improvements in biochemical-free survival and disease-free survival over RT alone.

ADT effectively slows the growth of prostate cancer cells, thereby enhancing therapeutic effectiveness of RT. Despite clinical gains, ADT induces rapid shifts in metabolic health including dyslipidemia, insulin resistance, and shifts in body composition favoring fat mass deposition and lean mass loss. Further, many patients report quality of life deterioration, particularly from increased fatigue and loss of vitality. These ADT metabolic changes occur rapidly, within 2-3 months of starting ADT and persist even after cessation of ADT.

**Table 1** summarizes these consistently observed changes from observational studies and meta analyses. Nearly all patients, even those with pre-ADT healthy weight and blood profiles, will experience some of these shifts, demonstrating a need for intervention.

Our overall research and clinical goals are to intercept or prevent the constellation of dyslipidemia, insulin resistance, weight gain and body composition shifts in these patients. These conditions are harder to treat than prevent since the body quickly becomes refractory to weight loss after a large gain has occurred. A small number of RCTs tested resistance or strength exercise during ADT and yielded modest improvements in overall muscle mass, fitness, quality of life and fatigue. However, most have been small, pilot studies and a lack of rigor may have contributed to inconsistent findings. No large trials have tested physical activity together with a dietary pattern (e.g., the DASH diet) shown to decrease cardiovascular disease and its antecedent risk factors that commonly develops in these patients. The AUA acknowledges the ADT-induced adverse effects but there are no proactive prevention guidelines and early intervention is not part of standard of care clinical protocols for patients on ADT. This represents an important gap that we will address first in this pilot followed by a fully powered RCT in an R01.

The study has the following primary **specific aims**:

1. Examine intervention effects on ADT-induced insulin resistance measured by HOMA-IR;
2. Examine intervention effects on ADT-induced changes in anthropometry (weight and waist circumference) and body composition (fat and lean mass).

**Exploratory aims:**

1. To explore intervention effects on blood lipids (total, HDL- and LDL-cholesterol) and HbA1c;
2. To explore intervention effects on patient reported outcomes;
3. To explore intervention effects on gut microbiome.

## 2. STUDY DESIGN

### 2.1 Overview

This is a pilot randomized controlled trial to investigate the effects of a 6-month nutrition and physical activity intervention on blood measures of lipids and insulin resistance, and anthropometry, body composition, and patient reported outcomes in n=20 newly diagnosed intermediate and high-risk prostate cancer patients

Table 1. Expected changes in blood biomarker and body composition measures due to initiation of ADT	
Measure	% change from ADT initiation
Blood biomarkers	
HbA1c, %	+ 1.3 - 4.7%
HOMA-IR	+11.6%
Total cholesterol, mg/dl	+ 0 - 9.0%
LDL cholesterol, mg/dl	+0 - 7.3%
HDL cholesterol, mg/dl	+7.6 - 11.3%
Triglycerides, mg/dl	+13.3 - 36.0%
Body composition markers	
Weight, kg	+1.8 - 2.4%
Waist circumference, cm	+1.4 - 3.9%
Total fat mass, kg	+11.0 - 12.0%
Total lean mass, kg	-2.5 - (-3.6)%

undergoing RT+ADT. Patients will be randomized to either:

[figure not shown]
1. Diet and physical activity intervention (modified DASH diet and aerobic activity and resistance training); or
2. Control (oral and written information based on general U.S. dietary and physical activity guidelines).

We will recruit and enroll patients from the VAPSHCS and UW prostate cancer clinics.

The study design is a six-month single blind, parallel-arm, randomized clinical trial with equal numbers in the intervention (n=10) and control (n=10) arms (**Figure 1**). Study activities in **Figure 1** take place at both the Fred Hutch Prevention Center and at the VAPSHCS. The intervention will be delivered by 10 in-person or virtual sessions with a Registered Dietitian, and on the same day, individual sessions with an Exercise Physiologist plus optional drop-in exercise

sessions. We have already established procedures for safe participant contact and procedures during COVID-19. Data collection includes self-reported lifestyle habits (diet, physical activity), objective measures of anthropometry/body composition (height, weight, waist circumference, dual x-ray absorptiometry (DXA)), biologic (blood biomarkers) and Patient Reported Outcomes (Health-Related Quality of Life and fatigue).

Figure 1. Study Design

### 3. ELIGIBILITY CRITERIA

Subjects with a diagnosis of intermediate or high risk localized prostate cancer who meet all of the inclusion and none of the exclusion criteria will be eligible for participation in this study. All races/ethnicities are eligible to participate.

#### 3.1 Inclusion Criteria

1. Age  $\geq$  40 years;
2. Histologically confirmed adenocarcinoma of the prostate, (D'Amico risk category intermediate or high risk, localized or locoregional);
3. Primary treatment is RT + ADT [Zoladex, Lupron, Degarelix, and other luteinizing hormone-releasing hormone (LHRH)-directed therapies] with standard RT dose and fractionation (anti-androgen monotherapy will not be allowed);
4. Physically able to undertake an exercise program

#### 3.2 Exclusion Criteria

1. Advanced, metastatic disease;
2. Planning to join a commercial/structured diet change or fitness program;
3. Have significant pre-existing T2D (poor glycemic control while on medication, defined as Hemoglobin A1c of  $\geq 10$  within the prior 12 months) or significant pre-existing CVD (myocardial infarction or stroke within prior six months);
4. Physician confirmed cognitive impairment or alcohol/narcotic abuse;

### 4. STUDY PROCEDURES

#### 4.1 Recruitment

**UW:** Clinic study staff will identify potential eligible participants from the UW urology clinic. Clinic study staff will pre-screen men to determine medical eligibility as listed in section 3. Recruitment efforts will be targeted towards medically eligible men living in the greater Seattle area. All of our recruitment messages and brochures will outline the parameters of the project and will stress the time commitment necessary in order to participate. Clinic study staff will approach eligible prospective participants during a clinic visit to tell them

about the study. Interested men will be asked to sign consent (Triple-A Consent for Contact UW) and their contact information to be sent to Fred Hutch for final eligibility screening and scheduling. Fred Hutch study staff will contact potential participants by phone to provide additional information about the study, answer question and confirm eligibility (Triple-A ScreeningScript\_V1). Interested participants will be scheduled for Clinic Visit 1 and asked to provide verbal consent to complete pre-visit 1 study activities (Triple-A\_VerbalConsentScriptPreStudy\_V1). Clinic Visit 1 will be scheduled to occur at Fred Hutch approximately 4 weeks of the first scheduled ADT dose. Once consented, participants will be mailed instructions to prepare for Clinic Visit 1 (Triple-A CV1 instructions, Triple-A Stool collection), a stool collection kit, Serving Size Booklet (Serving Size Booklet) and Food Record (Food Record) to complete prior to Clinic Visit 1.

**VAPSHCS:** Clinic study staff will identify potential eligible participants from the VA urology clinic. Clinic study staff will pre-screen men to determine medical eligibility as listed in section 3. Recruitment efforts will be targeted towards medically eligible men living in the greater Seattle area. Given the high proportion of minority patients at the VAPSHCS, we will make every effort to recruit eligible minority patients into the study. All of our recruitment messages and brochures will outline the parameters of the project and will stress the time commitment necessary in order to participate. Clinic study staff will approach eligible prospective participants either during a clinic visit or by phone to tell them about the study and confirm their eligibility. Interested men will be scheduled for Clinic visit 1 and study staff will ask potential participants to provide verbal consent to complete pre-visit 1 study activities. Clinic visit 1 will be scheduled to occur at the VA within approximately 4 weeks of the first scheduled ADT dose. Once consented, participants will be provided (or mailed) instructions to prepare for Clinic Visit 1, a stool collection kit, Serving Size Booklet and Food Record to complete prior to Clinic Visit 1.

#### 4.2 Clinic Visit 1

**UW (at Fred Hutch):** Fred Hutch study staff will review study procedures and confirm interest in participating in the study. Participant will be given the opportunity to ask questions and interested participants will sign the UW study consent and HIPAA(Triple-A UW consent; Triple-A HIPAA). Study staff will collect the participants' completed 4-day food record and stool sample (completed at home in preparation for Clinic Visit 1), measure height, weight and waist circumference, and collect fasting blood. In addition, participants will complete questionnaires on demographics/lifestyle characteristics (Triple-A demographic questionnaire), physical activity (Triple-A PA questionnaire) and quality of life/fatigue (Triple-A QOL questionnaire). Clinic staff will conduct a DXA scan and participants will be randomly assigned (via computerized program located within the Triple-A REDCap database) to either the intervention or control arm. After Clinic Visit 1 procedures are complete, participants randomized to the control arm will receive general healthy lifestyle instruction (Triple-A Control lifestyle instruction), while participants assigned to the intervention arm will receive an overview of the intervention goals (Triple-A Nutrition Intervention overview) and be scheduled for the first intervention session.

**VAPSHCS (at VAPSHCS):** VA study staff will review study procedures and confirm interest in participating in the study. Participant will be given the opportunity to ask questions and interested participants will sign the VA study consent and HIPAA. Study staff will collect the participants' completed 4-day food record and stool sample (completed at home in preparation for Clinic Visit 1), measure height, weight and waist circumference, and collect fasting blood. In addition, participants will complete questionnaires on demographics/lifestyle characteristics, physical activity and quality of life/fatigue. Clinic staff will conduct a DXA scan and participants will be randomly assigned (via a computerized program) to either the intervention or control arm. To randomize participants, study staff will use a computerized program located within the Triple-A REDCap database.

After Clinic Visit 1 procedures are complete, participants randomized to the control arm will receive general healthy lifestyle instruction. This instruction will be provided via teleconference by the Fred Hutch study nutritionist. Participants assigned to the intervention arm will receive an overview of the intervention goals (Triple-A Nutrition Intervention\_Orientation) and be scheduled for the first intervention session (which will occur at Fred Hutch). If requested, a participant may receive a copy of their DEXA scan results.

